7.3 Liver safety monitoring

Term	Percentage
GMOs	85%
Organic	75%
Natural	65%
Artificial	55%
Organic	50%
Natural	45%
Artificial	35%
Organic	30%
Natural	25%
Artificial	20%
Organic	15%
Natural	10%
Artificial	5%

7.4 Pregnancy reporting

To ensure patient safety, each pregnancy occurring after signing the informed consent must be reported to Novartis within 24 hours of learning of its occurrence. The pregnancy should be followed up to determine outcome, including spontaneous or voluntary termination, details of the birth, and the presence or absence of any birth defects, congenital abnormalities, or maternal and/or newborn complications.

11. **What is the primary purpose of the following statement?**

8 Data review and database management

8.1 Site monitoring

Before study initiation, at a site initiation visit or at an investigator's meeting, a Novartis representative will review the protocol and eCRFs with the investigators and their staff. During the study, the field monitor will visit the site regularly to check the completeness of patient records, the accuracy of entries on the eCRFs, the adherence to the protocol and to Good Clinical Practice, the progress of enrollment, and to ensure that investigational treatment is being stored, dispensed, and accounted for according to specifications. Key study personnel must be available to assist the field monitor during these visits.

The investigator must maintain source documents for each patient in the study, consisting of case and visit notes (hospital or clinic medical records) containing demographic and medical

11. **What is the primary purpose of the *Journal of Clinical Endocrinology and Metabolism*?**

[figure not shown]
information, laboratory data, electrocardiograms, and the results of any other tests or assessments. All information on eCRFs must be traceable to these source documents in the patient's file. The investigator must also keep the original informed consent form signed by the patient (a signed copy is given to the patient).

8.2 Data collection

8.3 Database management and quality control

[REDACTED]

[REDACTED]

[REDACTED]

[REDACTED]

[REDACTED]

[REDACTED]

[REDACTED]

[REDACTED]

8.4 Interim safety and PK data review

As described in [Section 3.1](#), Study design, [REDACTED]

[REDACTED], age cohorts will be enrolled sequentially, within each dose group, from age cohort 1 to 4. For each age cohort, 3 patients will be enrolled first into the low-dose group and if it is considered safe after review of all available safety and PK data (up to and including study day 5), then patients will be enrolled into the low-dose group for the succeeding age cohort. No patients will be enrolled into the high-dose group for a given age cohort until data from the low-dose group of that same age cohort and the high-dose group of the preceding age cohort is reviewed and it is considered safe to proceed. Data review is anticipated to include the following, when available:

- AEs and SAEs and their causal relationship to the study drug
- Hypotension events, dose adjustments and discontinuations
- Evidence of pharmacodynamic interactions between serelaxin and co-medications
- Vital signs, respiratory parameters and clinical assessments
- Blood chemistry, hematology, blood gas and serum lactate levels, and renal biomarkers (as available)
- PK

[REDACTED]

[REDACTED]

[REDACTED]

[REDACTED]

[REDACTED]

8.5 Adjudication Committee

Not required.

9 Data analysis

9.1 Analysis sets

The following analysis populations will be defined for the statistical analysis:

- Screened set (SCR) – All subjects who signed the informed consent.
- Enrolled set (ES) – All subjects to whom study treatment has been assigned.
- Safety set (SAF) – All subjects in the ES who were exposed to study drug regardless of the exposure duration, and have at least one post-baseline safety assessment. Of note, the statement that a subject had no adverse events also constitutes a safety assessment.
- The PK analysis set (PK) will include all subjects with at least one available valid (i.e. not flagged for exclusion) PK concentration measurement, who received any study drug and experienced no protocol deviations with relevant impact on PK data.

The number and percentage of subjects in the ES who completed the study and who discontinued the study, and the reason for discontinuation, will be presented for each age cohort and over all subjects, by dose group.

9.2 Patient demographics and other baseline characteristics

Subject demographics (age, age cohort, [REDACTED] sex, ethnicity, race, weight and height) and baseline characteristics [heart failure history, mode of ventilation (invasive, non-invasive, spontaneous breathing)] will be summarized by age cohort and overall for the ES. Screening [REDACTED] eGFR will be summarized with standard descriptive statistics. Medical history data will be summarized by age cohort and dose group and for all subjects. Continuous variables will be summarized using n, mean, median, standard deviation, minimum, maximum, and categorical variables will be summarized using frequency and percentage. [REDACTED]

9.3 Treatments

Overall study drug administration details will be summarized by age cohort and dose group (low-dose group, high-dose group) and for all subjects for the SAF population. This will include study drug administered (yes/no), reason study drug not administered, actual study drug received, and the number of days infused (one or two). The duration of study drug administration (in hours) and the total volume of study drug administered (estimated from the total time and rate of infusion) will be summarized by dose group and by age cohort as well as for all patients. In addition, the number of patients whose study medication dose was lowered

or discontinued prematurely, and the reasons for discontinuation, will be summarized by age cohort and dose group and for all subjects.

Concomitant medications and significant non-drug therapies, prior to and after the start date of treatment, respectively, will be summarized by therapeutic class, preferred term, age cohort and dose group for the SAF population.

9.4 Analysis of the primary variable(s)

There are two primary objectives for this study, the assessment of safety and tolerability and the assessment of pharmacokinetics.

The statistical methods for the assessment of safety and tolerability (rate of adverse events, routine assessment of laboratory parameters including those for renal function) are summarized in [Section 9.5.2](#). The statistical methods for the pharmacokinetics variables are discussed in this section.

9.4.1 Variable(s)

Pharmacokinetic parameters will include C_{ss} (steady state concentration, estimated by C_{16hr} , C_{32hr} and C_{48hr} for each dose level), and CL (clearance, estimated using the following equation: $CL = \text{Rate of infusion}/C_{ss}$). Refer to [Section 6.6.2](#) for time points for pharmacokinetic (PK) assessments.

9.4.2 Statistical model, hypothesis, and method of analysis

The PK parameters C_{ss} and CL will be mainly summarized descriptively by age cohort and dose within each dose group. A graphical presentation will be employed to show mean and individual RLX030 concentration-time profiles for each age cohort and each dose group.

The PK parameters C_{ss} and CL may be pooled across dose group (high/low-dose) within each age cohort and summarized as appropriate by dose level and age cohort for 10 $\mu\text{g}/\text{kg}/\text{day}$ and 30 $\mu\text{g}/\text{kg}/\text{day}$, respectively.

9.4.3 Handling of missing values/censoring/discontinuations

No imputation will be done for missing values at 16, 32 or 48 hours for the estimation of Css, or at any planned time points for the by-visit summaries. Only values recorded in the data base will be used for the by-visit summaries at these time point.

9.4.4 Supportive analyses

9.5 Analysis of secondary variables

9.5.1 Efficacy variables

Hemodynamic parameters (secondary)

Secondary endpoints will be assessed at baseline, prior to each dose escalation, and at 24 hr post end of infusion. Secondary endpoints will include an assessment of hemodynamic effects on routinely measured hemodynamic parameters as listed below:

- arterial BP
- central venous pressure (CVP)
- left atrial pressure (LAP) and pulmonary artery pressure (PAP – systolic and diastolic), if available
- central venous and arterial oxygen saturation
- urine output
- blood lactate levels

For arterial BP, CVP, LAP, PAP, central venous and arterial oxygen saturation, urine output and blood lactate levels, the absolute values at baseline and each time point (when these parameters are measured), as well as the change from baseline will be descriptively summarized by age cohort and dose group and for all patients.

[REDACTED]

[REDACTED]

[REDACTED]

[REDACTED]

[REDACTED]

[REDACTED]

[REDACTED]

[REDACTED]

9.5.2 Safety variables

Adverse events, SAEs and Death

Adverse events (AEs, SAEs and AEs leading to discontinuation) will be summarized by cohort and dose group and for all subjects in the SAF for the entire study period, during each of the 16 hour dose escalation periods and over the post infusion period. Adverse events (number and percent) will be presented by system organ class and MedDRA preferred term.

In addition, a summary of AEs by preferred term and severity, using the worst reported severity grade for each event for the subject, will be provided. The number and percentage of patients with AEs possibly related to study medication will be summarized by age cohort and dose group and for all patients as well. These summaries will be presented for the entire study period, during each of the 16 hour dose escalation periods and over the post infusion period, respectively.

Death (if any) will be summarized by system organ class and MedDRA preferred term as well. AEs, SAEs and death will be also presented in data listings at individual patient level.

Laboratory, vital signs, body weight and decreased blood pressure events

Laboratory data will be summarized by presenting shift tables using extended normal ranges (baseline to most extreme post-baseline value), summary statistics of raw data and change

[REDACTED]

[REDACTED]

from baseline (mean, confidence interval, median, standard deviation, 1st and 3rd quartiles Q1 and Q3) at each assessment time point by age cohort and dose group and for all subjects. Notably abnormal values for individual subjects will be flagged in data listings.

Vital sign data and clinical assessments (including HR, SBP and DBP, ventilation parameters etc. as described in [Section 6.5.2](#) excluding the efficacy variables specified in [Section 6.4.1](#)) will be descriptively summarized as appropriate by presenting absolute values and change from baseline at each assessment time point for each age cohort and dose group and for all patients. In addition, respiratory parameters including FiO₂, and oxygenation index (FiO₂×MAP)/PaO₂ (for patients on mechanical ventilation only), and PaO₂/FiO₂ ratio, will also be summarized by presenting absolute values and change from baseline at each assessment time point by age cohort, dose group and ventilation mode.

The absolute values and change from baseline at each visit in body weight will be summarized descriptively by age cohort and dose group and for all patients.

The number and proportion of patients who experience a confirmed blood pressure decrease event during study drug administration will be provided by dose level within each dose group and age cohort. Further details on confirmed blood pressure decrease events (including whether they result in study drug dose reduction or discontinuation) will be provided as well.

ECG

The ECG findings and central ECG data will be summarized as appropriate by age cohort and dose group and for all subjects in the SAF population.

9.5.3 Resource utilization

Not applicable

9.5.4 Pharmacokinetics

The pharmacokinetics data analysis is described in [Section 9.4](#).

9.5.5 Pharmacogenetics/pharmacogenomics

Not applicable

9.5.6 Biomarkers

[REDACTED]

9.5.7 PK/PD

[REDACTED]

[REDACTED]

9.6 Interim analyses

There will be no interim analysis for this study. However, there will be interim PK and safety data reviews by the PSRC. See [Section 3.1](#) for study design details.

9.7 Sample size calculation

Sample size is guided by feasibility in pediatric patient studies for assessment of safety, tolerability and pharmacokinetics.

The sample size planned for the high-dose group (10/30/100 µg/kg/day) per age cohort will be 6 subjects. With a sample size of 6 subjects per age cohort, receiving RLX030 at various doses, there is ~80% probability to observe an adverse event with an underlying occurrence rate of 24% at least once for each cohort and dose combination during the study. With a sample size of 3 subjects per age cohort, receiving RLX030 at various doses, there is ~56% probability to observe an adverse event with an underlying occurrence rate of 24% at least once for each cohort and dose combination during the study.

Data from 6 subjects will also provide ~80% probability for the 95% confidence intervals (CI) of geometric means of RLX030 Css to fall within the range of (68%U, 146%U), data from 3 subjects will provide ~80% probability for the 95% confidence intervals (CI) of geometric means of RLX030 Css to fall within the range of (39%U, 257%U), where U is the observed geometric mean, assuming a coefficient of variation of 30% [REDACTED]

[REDACTED] an additional 3 subjects will be enrolled into a low-dose group (3/10/30 µg/kg/day) in each age cohort. The purpose of this low-dose group is to further enhance the safety by collecting safety data at a starting dose of 3 µg/kg/day up to the adult efficacious dose of 30 µg/kg/day, before enrolling patients in the high-dose group.

These calculations were performed using nQuery.

10 Ethical considerations

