[REDACTED] A total duration of 48 hours is planned for the constant iv serelaxin infusion with dose escalations every 16 hours. A low-dose group and a high-dose group will be enrolled sequentially in every age cohort. During this 48-hour treatment period, the serelaxin dose rates to be administered are 3 $\mu\text{g}/\text{kg}/\text{day}$, 10 $\mu\text{g}/\text{kg}/\text{day}$ and 30 $\mu\text{g}/\text{kg}/\text{day}$ in the low-dose group; 10 $\mu\text{g}/\text{kg}/\text{day}$, 30 $\mu\text{g}/\text{kg}/\text{day}$ and 100 $\mu\text{g}/\text{kg}/\text{day}$ in the high-dose group [REDACTED]. These dose rates are anticipated to be safe in the pediatric population and are based on the dose range investigated in adults with AHF.

Thirty (30) male or female pediatric patients (minimum) will be enrolled in this study with 3 patients in each low dose group for age cohorts 1, 2, 3 and 4; and 6 patients in each high-dose group for age cohorts 3 and 4, and 3 (maximum 6) patients in each high dose group for age cohorts 1 and 2. The four age cohorts are as follows:

- Cohort 1: 6 to <18 years [3 low-dose patients, 3 high-dose patients (maximum 6)]
- Cohort 2: 1 to <6 years [3 low-dose patients, 3 high-dose patients (maximum 6)]
- Cohort 3: infants 1 month* to <1 year [3 low-dose patients, 6 high-dose patients]
- Cohort 4: neonates birth to <1 month* [3 low-dose patients, 6 high-dose patients]

*1 month = 30 days

[REDACTED]

[REDACTED]

[REDACTED]

Age cohorts will be enrolled sequentially from age cohort 1 to 4, within each dose group. For each age cohort, patients will be enrolled first into the low-dose group and if it is considered safe after a review of all available safety and pharmacokinetic (PK) data, up to and including study day 5, then patients will be enrolled into the low-dose group for the succeeding age cohort. Patients cannot be enrolled into the high-dose group for a given age cohort until data from the low-dose group of that same age cohort and the high-dose group of the preceding age cohort (where present) has been reviewed and it is considered safe to proceed.

[REDACTED]

Enrollment within each dose group will be temporarily stopped 4 times for the low dose group and 3 times for the high dose group during the study for a review of safety and PK data as follows:

Low Dose Group

- 1st enrollment stop for low-dose, safety and PK data review after completion (up to day 5) of 3 low-dose patients in age cohort 1

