5.5.4 Instructions for prescribing and taking study treatment

The study drug infusion will begin after informed consent has been given in writing (ICF signed by parent/guardian and patient consent or assent where applicable) and the completion of all screening/baseline procedures, and will continue for a total 48 hours (16 hour infusion per dose level). The study drug should be administered via a peripheral or central iv line or port, as soon as possible, but no more than 5 hours after enrollment (i.e. confirmation of eligibility for the study and the baseline IRT contact where a medication number is assigned). Compatible filters and syringes which have been tested and qualified for use with serelaxin, must be used to prepare and administer the study drug. [REDACTED]

The required amount of study drug will be calculated for each patient for each dose titration level and will be withdrawn from the 6 mL vials (with 3.5 mL fill) contained in the study drug kits, added to a syringe of 5% dextrose solution (10% dextrose may also be considered), and then infused at a constant rate over a period of 16 hours for each titration level. [REDACTED]

Each dose level is infused over 16 hours. Dose escalation should only occur if

- the patient does not fulfill any requirement for dose adjustment or discontinuation (see [Section 5.5.5](#) Permitted dose adjustments of study treatment) on the preceding infusion rates, and
- the investigator considers dose escalation to be safe based on his global clinical assessment, including an evaluation of the patient's hemodynamic status (including physical examination ([Section 6.5.1](#)), vital signs and hemodynamic parameters, arterio-venous oxygen extraction) and a comparison of his/her current condition with the one before starting serelaxin and before the previous dose escalation.

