In addition, SAEs in screen failure patients will be listed at the individual patient level.

11 Other data

Other data will be listed at the individual patient level as appropriate. The following data will be listed for the SAF, and listings marked with “*” will be subject to data availability:

- Local lab (including chemistry, hematology and urinalysis)
- Central lab (including chemistry and hematology)
- Vital signs and clinical assessment
- Ventilation/respiratory parameters (if on mechanical ventilation)
- * Systolic Blood Pressure Decrease Event (SBPDE)
- * Vital signs – SBPDE monitoring
- * Ventilation/respiratory parameters – SBPDE monitoring
- * Vital signs – AE suggestive of Worsening Heart Failure (WHF) monitoring
- * Ventilation/respiratory parameters – AE suggestive of Worsening Heart Failure (WHF) monitoring
- Echocardiography
- [REDACTED]
- ECG
- [REDACTED]
- [REDACTED]

[REDACTED] eGFR (as part of the central laboratory data) will be calculated using the Schwartz formula (Schwartz et al. 2009): eGFR (mL/min/1.73m²) = 0.41 x height (cm)/serum creatinine (mg/dL).

Mean arterial pressure, derived as [(2 x DBP) + SBP] ÷ 3 (Cywinski 1980), will be included in listings of the vital signs data. Notably abnormal vital signs (SBP, DBP, HR and RR) [REDACTED] will be noted in data listings.

12 Interim analyses

There will be no formal interim analysis for this study. However, there will be interim PK and safety data reviews by the Pediatric Safety Review Committee (PSRC). See Section 3.1 of the study protocol for study design details.

[REDACTED]

13 Sample size and power considerations

Sample size is guided by feasibility in pediatric patient studies for assessment of safety, tolerability and pharmacokinetics.

The sample size planned for the high-dose group (10/30/100 µg/kg/day) per age cohort will be 6 subjects or 3 subjects (see Section 3.1 of the study protocol v04 for the study design details). With a sample size of 6 subjects per age cohort, receiving RLX030 at various doses, there is ~80% probability to observe an adverse event with an underlying occurrence rate of 24% at least once for each cohort and dose combination during the study. With a sample size of 3 subjects per age cohort, receiving RLX030 at various doses, there is ~56% probability to observe an adverse event with an underlying occurrence rate of 24% at least once for each cohort and dose combination during the study.

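### Protocol 9.7 gives 6 high-dose subjects for every age cohort, but the design plans 3 (maximum 6) in cohorts 1 and 2, so ~80% AE detection reads as planned where ~56% applies

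*Protocol*

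**What the plan says.** Protocol 9.7 opens its justification with a high-dose size that "per age cohort will be 6 subjects". It then gives two detection probabilities for an adverse event with a true rate of 24%: ~80% with 6 subjects and ~56% with 3. Each is described as the chance of seeing the event "at least once for each cohort and dose combination during the study". It also gives two ranges for the 95% confidence interval of the geometric mean Css: (68%U, 146%U) for 6 subjects and (39%U, 257%U) for 3. The only group of 3 that 9.7 identifies is the additional low-dose group in each cohort.

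Protocol 3.1 plans different numbers. In the two older cohorts the high-dose plan is "3 (maximum 6) patients in each high dose group for age cohorts 1 and 2". The larger size is reserved for the two younger cohorts, where the text reads "6 patients in each high-dose group for age cohorts 3 and 4". Every low-dose group has 3 patients. The synopsis agrees, and both give 30 as the minimum total.

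SAP section 13 repeats the calculations but words the high-dose size as "per age cohort will be 6 subjects or 3 subjects", followed by a reference to protocol 3.1.

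Protocol 5.5.4 makes each move to a higher dose level conditional ("Dose escalation should only occur if", followed by two criteria). Section 5.5.5 allows the infusion rate to be reduced or the infusion stopped.

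**The concern.** Someone who reads 9.7 alone will take 6 as the planned high-dose size everywhere, attach ~80% and the narrower Css range to the high-dose group in all four cohorts, and attach ~56% and the wider range to the low-dose groups. For cohorts 1 and 2 that is the wrong pairing.

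Section 9.7 rests the sample size on feasibility, and these figures are the quantitative support it offers. They determine how much weight an absence of events can carry. The high-dose safety and PK reviews for cohorts 1 and 2 are set in 3.1 after 3 patients, and data from any further patients go to the next available review meeting. The review that opens high dosing in the next younger cohort can therefore rest on n = 3.

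A second, smaller gap is that 9.7 does not say whether its probabilities assume that every planned subject receives each dose.

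**Working it through.** **Inputs.** True AE rate 24%, group sizes 6 and 3, and Css coefficient of variation 30% (protocol 9.7). Low-dose n of 3 in each cohort; high-dose n of 3, 3, 6, 6 in cohorts 1 to 4; minimum total 30 (protocol 3.1).

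**Total sample size.**
- Design in 3.1: 4 × 3 + (3 + 3 + 6 + 6) = 12 + 18 = 30, the stated minimum.
- First sentence on size in 9.7: 4 × 3 + 4 × 6 = 12 + 24 = 36. This equals the design only if cohorts 1 and 2 are both expanded to their maximum.

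**Detection probability.** P(at least one event) = 1 − (1 − 0.24)^n.
- n = 6: 1 − 0.76^6 = 80.7% (stated ~80%).
- n = 3: 1 − 0.76^3 = 56.1% (stated ~56%).

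Both reproduce. In the other direction, the true rate that gives 80% detection is 1 − 0.2^(1/n): 23.5% for n = 6 and 41.5% for n = 3.

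**Css range.** Half-width on the log scale = t(0.975, n−1) × 0.30 × √[χ²(0.80, n−1)/(n−1)] / √n, taking the log-scale SD as 0.30.
- n = 6: 0.380, giving (68.4%U, 146.2%U); stated (68%U, 146%U).
- n = 3: 0.945, giving (38.9%U, 257.4%U); stated (39%U, 257%U).

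Both reproduce. With the SD taken as √ln(1 + 0.30²) = 0.294, the ranges are (68.9%U, 145.1%U) and (39.6%U, 252.2%U), which is no material change.

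**Which figure belongs to which planned group.**

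| Group | Planned n | Detection at 24% | Css range |
|---|---|---|---|
| Low dose, cohorts 1–4 | 3 | 56.1% | (39%U, 257%U) |
| High dose, cohorts 1–2 | 3 (maximum 6) | 56.1% (80.7% only if expanded to 6) | (39%U, 257%U); (68%U, 146%U) only if expanded to 6 |
| High dose, cohorts 3–4 | 6 | 80.7% | (68%U, 146%U) |

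**Conditional escalation.** Three levels of 16 hours fill the 48 hours, so a patient held once at a level cannot reach the third. If one patient does not reach a given level, detection there falls to 1 − 0.76^5 = 74.6% (from n = 6) or 1 − 0.76^2 = 42.2% (from n = 3). The visible text gives no expected fraction reaching each level. As an assumed range, if a fraction r of subjects reaches the level, detection is 1 − (1 − 0.24r)^n. For r = 80%, 67% and 50% this gives 72%, 65% and 54% with n = 6, and 47%, 41% and 32% with n = 3.

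**The case against.** The strongest reply is that 9.7 contains no numerical error and hides nothing. The ~80% is explicitly tied to 6 subjects, the next sentence gives ~56% for 3, both Css ranges are given, and the design has exactly these two group sizes. The later document, SAP 13, already words the high-dose size as 6 or 3 and points to 3.1, where n is listed by cohort. All of that stands. A reader might infer that 9.7 promises ~80% in every cohort and dose cell, or that its figures are wrong. The documents do not support either reading.

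What the reply does not remove is the sentence naming 6 for every cohort. It contradicts 3.1, and nothing in the visible text of 9.7 links the n = 3 figures to a high-dose group.

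On escalation, cohort and dose combination is not defined. If it means age cohort by dose group, n is 6 or 3 whatever happens to escalation, and the upper-bound remark does not apply to the AE figures. If it means dose level, it does. Section 9.5.2 reports AEs by 16-hour escalation period and blood pressure decrease events by dose level within dose group and cohort, so the second reading is natural enough to need a sentence.

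One might also add low- and high-dose patients together at the two shared dose levels to obtain larger cells. The visible protocol text mentions such pooling only for Css and CL (9.4.2), so it cannot be assumed for AEs.

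Three limits on the consequences are fair. No hypothesis test or escalation threshold in the visible text depends on these probabilities. The study ended early, and SAP section 1 says PK parameters will not be provided for the abbreviated report, so the Css precision supports no output there. Text is redacted near both statements, and clarifying words cannot be excluded; the visible sentence in 9.7 would still disagree with 3.1.

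**Conclusion.** The high-dose sample size in protocol 9.7 is wrong as written for cohorts 1 and 2: 6 against a planned 3 (maximum 6), implying 36 patients where the stated minimum is 30. The probabilities and ranges are correct for the sizes they name. The defect is that they are not assigned to cohorts, so ~80% and (68%U, 146%U) read as the planned high-dose figures in two cohorts where 56.1% and (39%U, 257%U) apply. The difference is about 25 percentage points of detection (80.7 − 56.1 = 24.6), or a detectable rate of 41.5% rather than 23.5%.

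This rests on the 24% rate and 30% CV that the protocol states, and on cohorts 1 and 2 enrolling the planned 3; if both are expanded to 6, the n = 6 figures apply there as well. The upper-bound point is conditional on reading the AE claim by dose level. It applies to every level reached by escalation, not only the highest.

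**What to change.** In protocol 9.7, replace the sentence on high-dose size with: 6 subjects in cohorts 3 and 4, and 3 (maximum 6) in cohorts 1 and 2. Then state:

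- ~80% and (68%U, 146%U) apply to the high-dose group in cohorts 3 and 4, and in cohorts 1 and 2 only if expanded to 6;
- ~56% and (39%U, 257%U) apply to the high-dose group in cohorts 1 and 2 at the planned 3, and to all low-dose groups;
- at each dose level reached by escalation, the figures assume that all planned subjects receive that dose, and so are upper bounds there.

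SAP 13 already has the right n and the reference to 3.1. It needs only the same mapping and the same assumption.

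The cost is wording in two places: no extra patients and no new calculation. The drawback is that the stated figures for the high-dose group in cohorts 1 and 2 become visibly less favourable.
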